Subjects will be asked to stay at the study site for the first 24 h after the injection because multiple blood samples are to be collected over this period.

Regardless of the group/cohort to which a volunteer has been assigned, s/he will be followed-up for 50 days during which 16 visits will be performed.

Stage II

Stage II of the study aims to further evaluate pharmacokinetics, pharmacodynamics and safety of subcutaneous and intravenous injections of BCD-131 at a dose which ensures PD effects similar to those of the closest analogues (Mircera[®], Aranesp[®]) given as subcutaneous injections at therapeutic doses. For this purpose, 12 volunteers will be included in the study after they have signed an informed consent form, completed an examination at screening (no more than 14 days) and received the approval of the investigator confirming their eligibility for the study.

After having been randomized in a 1:1 ratio, the volunteers will be assigned to 2 groups.

- Six volunteers in Group 1 will receive a single intravenous injection of BCD-131 at a dose established at stage I of the study (Day 1).
- Six volunteers in Group 2 will receive a single subcutaneous injection of BCD-131 at a dose established at stage I of the study (Day 1).

Subjects will be asked to stay at the study site for the first 24 h after the injection because multiple blood samples are to be collected over this period. Regardless of the group/cohort to which a volunteer has been assigned, s/he will be followed-up for 50 days during which 16 visits will be performed.

3.2 Time Points for Blood Sampling to Evaluate PK at Stage I of the Study

In the groups of volunteers receiving BCD-131 and Mircera[®], blood sampling for the PK evaluation will be performed as follows:

1. PK1-1 — 5 min before the injection of BCD-131/Mircera[®]
2. PK2-1 — 30 ± 5 min after the injection of BCD-131/Mircera[®]
3. PK3-1 — $2 \text{ h} \pm 10 \text{ min}$ after the injection of BCD-131/Mircera[®]
4. PK4-1 — $8 \text{ h} \pm 15 \text{ min}$ after the injection of BCD-131/Mircera[®]
5. PK5-1 — $24 \text{ h} \pm 20 \text{ min}$ after the injection of BCD-131/Mircera[®]
6. PK6-1 — $48 \text{ h} \pm 30 \text{ min}$ after the injection of BCD-131/Mircera[®]
7. PK7-1 — $72 \text{ h} \pm 30 \text{ min}$ after the injection of BCD-131/Mircera[®]
8. PK8-1 — $96 \text{ h} \pm 60 \text{ min}$ after the injection of BCD-131/Mircera[®]
9. PK9-1 — $120 \text{ h} \pm 60 \text{ min}$ after the injection of BCD-131/Mircera[®]

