10. PK10-1 — $168 \text{ h} \pm 60 \text{ min}$ after the injection of BCD-131/Mircera[®]

11. PK11-1 — 216 h ± 120 min after the injection of BCD-131/Mircera®
12. PK12-1 — 288 h ± 120 min after the injection of BCD-131/Mircera®
13. PK13-1 — 336 h ± 120 min after the injection of BCD-131/Mircera®
14. PK14-1 — 504 h ± 120 min after the injection of BCD-131/Mircera®
15. PK15-1 — 672 h ± 120 min after the injection of BCD-131/Mircera®
16. PK16-1 — 840 h ± 120 min after the injection of BCD-131/Mircera®
17. PK17-1 — 1008 h ± 120 min after the injection of BCD-131/Mircera®
18. PK18-1 — 1176 h ± 120 min after the injection of BCD-131/Mircera®

In the group of volunteers receiving Aranesp®, blood sampling for the PK evaluation will be performed as follows:

1. PK1-1 — 5 min before the injection of Aranesp®
2. PK2-1 — 30 ± 5 min after the injection of Aranesp®
3. PK3-1 — 2 h ± 10 min after the injection of Aranesp®
4. PK3-1 — 8 h ± 15 min after the injection of Aranesp®
5. PK5-1 — 16 h ± 20 min after the injection of Aranesp®
6. PK6-1 — 24 h ± 20 min after the injection of Aranesp®
7. PK7-1 — 36 h ± 30 min after the injection of Aranesp®
8. PK8-1 — 48 h ± 30 min after the injection of Aranesp®
9. PK9-1 — 72 h ± 30 min after the injection of Aranesp®
10. PK10-1 — 96 h ± 60 min after the injection of Aranesp®
11. PK11-1 — 120 h ± 60 min after the injection of Aranesp®
12. PK12-1 — 168 h ± 60 min after the injection of Aranesp®
13. PK13-1 — 216 h ± 120 min after the injection of Aranesp®
14. PK14-1 — 288 h ± 120 min after the injection of Aranesp®
15. PK15-1 — 336 h ± 120 min after the injection of Aranesp®
16. PK16-1 — 504 h ± 120 min after the injection of Aranesp®
17. PK17-1 — 672 h ± 120 min after the injection of Aranesp®
18. PK18-1 — 840 h ± 120 min after the injection of Aranesp®

19. PK19-1 — 1008 h ± 120 min after the injection of Aranesp®
20. PK20-1 — 1176 h ± 120 min after the injection of Aranesp®

3.3 Time Points for Blood Sampling to Evaluate PK at Stage II of the Study

1. PK1-2 — 5 min before the injection of BCD-131
2. PK2-2 — 15 ± 3 min after the injection of BCD-131
3. PK3-2 — 30 ± 5 min after the injection of BCD-131
4. PK4-2 — 60 ± 5 min after the injection of BCD-131
5. PK5-2 — 2 h ± 10 min after the injection of BCD-131
6. PK6-2 — 4 h ± 15 min after the injection of BCD-131
7. PK7-2 — 8 h ± 15 min after the injection of BCD-131
8. PK8-2 — 24 h ± 20 min after the injection of BCD-131
9. PK9-2 — 48 h ± 30 min after the injection of BCD-131

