4. EVALUATION CRITERIA

4.1 Endpoints to Evaluate Single-Dose Pharmacokinetics

Primary endpoint

- $AUC_{0-1176\text{ h}}$ (area under the concentration vs. time curve from the moment of injection to 1176 h [Day 50 of follow-up]) and $AUC_{0-\infty}$ (to infinity).

Secondary endpoints

- C_{\max} (maximum serum concentration),
- T_{\max} (time to C_{\max}),
- $T^{1/2}$ (half-life),

- k_{el} (elimination constant),
- CL (total clearance).

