8.4. The data conversion

Pharmacokinetic parameters

Based on determined concentrations in blood a number of the pharmacokinetic parameters will be calculated for the study drug:

1. **AUC₍₀₋₁₁₇₆₎**— area under the plasma concentration curve from administration to 1176 h:

- At stage I for BCD-131 and Mircera® products:

$$AUC_{(0-1176)} = \sum_{p=2}^{18} \frac{(C_p + C_{p-1}) * (t_p - t_{p-1})}{2},$$

where C_p – plasma concentration at the moment t_p (hours); $t_p \in \{0; 0.5; 2; 8; 24; 48; 72; 96; 120; 168; 216; 288; 336; 504; 672; 840; 1008; 1176\}; p=1, \dots, 18$

- At stage I for Aranesp® product:

$$AUC_{(0-1176)} = \sum_{p=2}^{20} \frac{(C_p + C_{p-1}) * (t_p - t_{p-1})}{2},$$

where C_p – plasma concentration at the moment t_p (hours); $t_p \in \{0; 0.5; 2; 8; 16; 24; 36; 48; 72; 96; 120; 168; 216; 288; 336; 504; 672; 840; 1008; 1176\}; p=1, \dots, 20$

- At stage II:

$$AUC_{(0-1176)} = \sum_{p=2}^{21} \frac{(C_p + C_{p-1}) * (t_p - t_{p-1})}{2},$$

where C_p – plasma concentration at the moment t_p (hours); $t_p \in \{0; 0.25; 0.5; 1; 2; 4; 8; 24; 48\}$

72; 96; 120; 168; 216; 288; 336; 504; 672; 840; 1008; 1176}; $p=1, \dots, 21$

2. C_{max} - maximum plasma concentration.
3. T_{max} - time until C_{max} is reached.
4. **Terminal rate constant (k_{el} , elimination constant)** will be calculated for the plasma concentration curve during the terminal log-linear phase by regression.
5. **AUC_(0-∞)** - area under the plasma concentration curve from administration to infinity:

$$AUC_{(0-\infty)} = AUC_{(0-1176)} + \frac{C_{1176}}{k_{el}},$$

where C_{1176} - plasma concentration at the moment 1176 h; k_{el} - elimination constant.

6. **Plasma concentration half-life ($T_{1/2}$)** will be calculated as:
 $T_{1/2} = \frac{\ln(2)}{k_{el}}$, where k_{el} - elimination constant.
7. **Total clearance (CL)** will be calculated as:

$$CL = \frac{D}{AUC_{(0-1176)}}, \quad \text{where } D \text{ - single dose of the drug product.}$$

Pharmacodynamic parameters

Based on reticulocyte counts and on hemoglobin values a number of key pharmacodynamic parameters will be calculated:

1. **AUEC₍₀₋₁₁₇₆₎** - (area under effect curve from the moment of injection to 1176 h [Day 50 of follow-up]) based on the change in the absolute reticulocyte count after a single-dose injection of the drug product::

$$AUEC_{(0-1176)} = \sum_{p=2}^{15} \frac{(C_p + C_{p-1}) * (t_p - t_{p-1})}{2},$$

where C_p the absolute reticulocyte count at the moment t_p (hours);

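### One linear AUC formula, starting from the pre-dose sample, serves both stage II routes; it slightly overstates intravenous AUC and so understates intravenous clearance

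*SAP*

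**What the plan says.** Stage II randomises 12 volunteers 1:1 by route. SAP 3.1 states: "Six volunteers in Group 1 will receive a single intravenous injection of BCD-131"; the other six receive it subcutaneously.

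SAP 8.4 defines AUC(0-1176) as the "area under the plasma concentration curve from administration to 1176 h" and gives a single stage II formula, with no distinction by route: the sum over p = 2 to 21 of (C_p + C_{p-1})(t_p − t_{p-1})/2. The time set begins "0; 0.25; 0.5; 1; 2; 4; 8; 24; 48" and continues "72; 96; 120; 168; 216; 288; 336; 504; 672; 840; 1008; 1176", which makes 21 times. SAP 3.3 lists 21 samples. The first is "PK1-2 — 5 min before the injection of BCD-131" and the second is "PK2-2 — 15 ± 3 min after the injection of BCD-131", so by count and order the t = 0 term is the pre-dose sample.

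The same section estimates k_el "during the terminal log-linear phase by regression", so it treats the end of the curve as exponential. It then uses AUC(0-1176) in two further parameters: AUC(0-∞) adds C_1176/k_el to it, and CL divides the dose by it. SAP 4.1 makes the "area under the concentration vs. time curve from the moment of injection to 1176 h", together with AUC(0-∞), the primary PK endpoint.

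The SAP gives no estimate of the concentration at t = 0 after IV dosing, no logarithmic trapezoid and no separate IV rule. The protocol text gives no AUC formula.

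**The concern.** For an SC injection a pre-dose value is the right start, because the drug has not yet been absorbed. After an IV bolus the concentration is highest at t = 0, so a first trapezoid rising from the pre-dose value loses area.

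From then on an IV curve only falls. An exponential decline is convex, so a straight line between two samples lies above it, and every interval is overstated. The stage II gaps are 16 h after the 8 h sample, 24 to 72 h until 336 h, and 168 h from there on.

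At stake are the AUC and CL of the six IV volunteers, the trial's only intravenous data on this product. The bias has the same sign in every volunteer, so averaging does not remove it. One stage II objective is to establish an IV dose for phase II, and these parameters would be among its inputs.

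**Working it through.** The plan states no AUC, half-life or expected error, so there is no figure of its own to reproduce. The check applies the SAP formula to curves with a known integral.

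**Inputs.** The 21 stage II times and the linear formula come from SAP 8.4. Assumptions: IV bolus, pre-dose value 0, initial concentration 1, half-life h from 10 to 130 h.

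**Formulas.** With k = ln 2/h and C(t) = exp(−kt), the exact AUC(0-1176) is (1 − exp(−1176k))/k. The SAP value is the linear sum with C = 0 at t = 0. The pre-dose start removes 0.5 × 0.25 × 1 = 0.125 from the first trapezoid; divided by the exact AUC, this is its share of the error. The rest comes from the straight lines.

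**Example, h = 100 h.**
- Exact 144.228, SAP 146.397; 146.397/144.228 − 1 = +1.50%.
- Pre-dose start: −0.125/144.228 = −0.09%. Straight lines: +1.59%.
- One wide interval, 336 to 504 h: concentrations 0.0974 and 0.0304. The trapezoid is 84 × (0.0974 + 0.0304) = 10.73, against an exact 9.67.

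**All half-lives, IV.**

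| h (h) | Exact | SAP | Pre-dose start | Straight lines | Net AUC error | CL error |
|---|---|---|---|---|---|---|
| 10 | 14.427 | 15.485 | −0.87% | +8.2% | +7.3% | −6.8% |
| 20 | 28.854 | 29.766 | −0.43% | +3.6% | +3.2% | −3.1% |
| 30 | 43.281 | 44.167 | −0.29% | +2.3% | +2.1% | −2.0% |
| 50 | 72.135 | 73.277 | −0.17% | +1.8% | +1.6% | −1.6% |
| 100 | 144.228 | 146.397 | −0.09% | +1.6% | +1.5% | −1.5% |
| 130 | 187.196 | 189.707 | −0.07% | +1.4% | +1.3% | −1.3% |

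The CL error is exact/SAP − 1, over the same 0 to 1176 h window.

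**With a distribution phase.** For bi-exponential curves (fast half-life 0.5 to 5 h carrying 30% to 70% of the initial concentration, terminal half-life 20 to 130 h), the net error runs from +1.3% to +6.8%. The maximum is at 5 h, 70% and 20 h.

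**SC curves under the same rule.** One-compartment, absorption half-life 12, 24 and 45 h:

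| h (h) | SC AUC error | SC/IV ratio error, present rule |
|---|---|---|
| 20 | −1.0% to +0.4% | −4.1% to −2.7% |
| 50 | +0.2% to +1.3% | −1.4% to −0.3% |
| 100 | +0.9% to +1.4% | −0.6% to −0.1% |
| 130 | +0.9% to +1.2% | −0.5% to −0.1% |

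**After the change, IV only.** C(0) is taken as C(0.25)²/C(0.5), which is log-linear back-extrapolation. Each falling interval contributes (t_p − t_{p-1})(C_{p-1} − C_p)/ln(C_{p-1}/C_p). The mono-exponential error is 0.0% at every half-life, by construction. The bi-exponential error fell in every case run. The largest remaining error was 2.6% (fast half-life 3.5 h, 70%, terminal 20 h), where the present rule gives +6.5%.

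Correcting t = 0 alone would leave the straight-line column as the net error: 8.2% instead of 7.3% at 10 h, and 1.59% instead of 1.50% at 100 h.

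**The case against.** The linear trapezoid is explicit, reproducible and applied alike to every arm. The larger errors need half-lives that the documents do not give; at 50 h or more, a mono-exponential curve is off by 1.6% at most. With six volunteers per route and descriptive stage II objectives, a shift of that size is unlikely to change a conclusion. All of this stands, and it is why the point is minor. It does not remove the error: the AUC formula is explicit, and the SAP 8.2 allowance for adding statistical methods does not alter it.

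Three stronger readings are tempting, and none is supported.

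- **That the pre-dose start is the main fault.** It is worth −0.07% to −0.9%, acts against the larger error, and assumes a bolus; no injection duration is stated. If the assay also reads endogenous erythropoietin, the pre-dose value exceeds zero and the loss is smaller.
- **That only the IV group is affected, because rising and falling parts offset on an SC curve.** At 100 h the SC error is +0.9% to +1.4%, against +1.5% for IV.
- **That the SC/IV comparison is compromised and one log rule for both routes would repair it.** The plan names no SC/IV AUC ratio, margin or specific hypothesis. At long half-lives the two errors nearly cancel. The ratio is 3% to 4% low at 20 h, but that half-life is assumed. Using linear-up/log-down on both routes leaves the ratio unchanged or worse from 30 h up: at 100 h its error becomes −0.8% to −0.7%. It also moves SC AUC to between −0.4% and −1.6% at 50 h or more, and to −5.1% at 10 h with 12 h absorption.

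**Conclusion.** The point holds as a minor one, limited to IV AUC and CL. As written, the stage II rule begins the IV curve at a pre-administration value and integrates an exponential decline with straight lines. The net effect was upward in every case run, so CL is understated. The overstatement becomes material only if the half-life is short or there is a marked distribution phase.

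These sizes rest on an assumed half-life and curve shape, bolus injection, a pre-dose value of zero, and sampling at nominal times. The direction of the straight-line error rests only on a convex decline, which the SAP itself assumes for the terminal phase.

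**What to change.** In SAP 8.4, give the stage II IV group its own AUC rule:

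1. Concentration at t = 0: log-linear back-extrapolation from the 0.25 and 0.5 h samples, or the 0.25 h value if those two do not fall. State that this is part of the parameter's definition, so that it does not collide with the no-substitution rule in SAP 8.3.
2. Logarithmic trapezoid wherever concentration falls, and linear elsewhere (including any interval that ends at zero, where the log form is undefined).
3. Make both changes together.
4. Carry the result into IV AUC(0-∞) and CL.
5. Keep the linear rule for SC curves. Report the linear IV AUC as a check, and use it for any SC/IV comparison.

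The cost is a short paragraph and a few lines of R, which SAP 8.1 already provides for; no new samples or subjects are needed.

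The downside is two AUC conventions within stage II. If the new IV AUC were set against the linear SC AUC at half-lives of 100 h or more, the ratio would be about 1% high (0.9% to 1.4%), against 0.1% to 0.6% low now. At 20 h the mixed ratio would be closer to the truth (−1.0% to +0.4%, against −4.1% to −2.7%). Because the half-life is not known in advance, the SAP should fix which IV AUC enters a comparison before the data are seen.

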7. STATISTICAL ANALYSIS OF POPULATION

Pharmacokinetics analysis

The pharmacokinetics (PK) analysis will include data of all volunteers who have received one dose of BCD-131 or reference drugs. If a subject has had more than two PK serum samples missed / lost / spoilt and skipped blood sampling time points more than twice, his/her data will not be included in the PK analysis.

Pharmacodynamics analysis

The pharmacodynamics (PD) analysis will include data of all volunteers who have received one dose of BCD-131 or reference drugs. If a subject has had more than two PK serum samples missed / lost / spoilt and skipped blood sampling time points more than twice, his/her data will not be included in the PD analysis.

Safety analysis

The safety analysis will include all patients who have received one dose of the test/reference drug.

Immunogenicity analysis

The immunogenicity analysis will include data of all volunteers who have received one dose of BCD-131 or reference drugs. If a subject has had serum samples taken on Day 1 and Day 50 missed / lost / spoilt, his/her data will not be included in the immunogenicity analysis.

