$t_p \in \{ 0; 24; 48; 72; 96; 120; 168; 216; 288; 336; 504; 672; 840; 1008; 1176 \}; p=1, \dots, 15$

2. **AUEC₍₀₋₁₁₇₆₎** - (area under effect curve from the moment of injection to 1176 h [Day 50 of follow-up]) based on the change in the Hb level in the blood after a single-dose injection of the drug product:

$$AUEC_{(0-1176)} = \sum_{p=2}^{15} \frac{(C_p + C_{p-1}) * (t_p - t_{p-1})}{2},$$

where C_p the Hb level at the moment t_p (hours);

$t_p \in \{ 0; 24; 48; 72; 96; 120; 168; 216; 288; 336; 504; 672; 840; 1008; 1176 \}; p=1, \dots, 15$

3. AC-E_{max} (absolute maximum increase in the test parameter vs. baseline) based on the change in the absolute reticulocyte count in the blood after a single-dose injection of the drug product.
4. AC-E_{max} (absolute maximum increase in the test parameter vs. baseline) based on the change in the Hb level in the blood after a single-dose injection of the drug product.

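### SAP 8.4 fixes the AUC and AUEC time axis at nominal hours and has no rule for off-schedule draws; the effect is small and the correction costs only wording

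*SAP*

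**What the plan says.** - **PK areas.** SAP 8.4 defines AUC0-1176 as a sum of linear trapezoids, "where C_p – plasma concentration at the moment t_p (hours"), and then limits t_p to a closed set of hours. For stage I BCD-131 and Mircera that set, after 0, is "0.5; 2; 8; 24; 48; 72; 96; 120; 168; 216; 288; 336; 504; 672; 840; 1008; 1176". Aranesp and stage II have their own lists of the same kind.
- **PD areas.** Both AUECs (reticulocytes and Hb) use the same construction, on 0 and then "24; 48; 72; 96; 120; 168; 216; 288; 336; 504; 672; 840; 1008; 1176".
- **Windows.** SAP 3.2 and 3.3 give every post-dose PK draw a tolerance. The narrowest is "PK2-2 — 15 ± 3 min after the injection of BCD-131". From 216 h onward every tolerance is ±120 min, for example "PK14-1 — 504 h ± 120 min after the injection of BCD-131/Mircera" and "PK18-1 — 1176 h ± 120 min after the injection of BCD-131/Mircera".
- **Exclusion.** SAP 7 drops a volunteer from the PK and PD sets for "more than two PK serum samples missed / lost / spoilt and skipped blood sampling time points more than twice". It does not mention a sample that was drawn, but late.
- **Other time-based quantities.** SAP 8.4 gives no time basis for T_max or for the terminal regression that yields k_el.
- **Data handling.** SAP 8.3 covers queries, outliers and missing or spurious data, but not sampling time. SAP 10 declares no deviation from the protocol, and the protocol's analysis sections contain no actual-time rule.

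**The concern.** The plan expects draws to miss their scheduled hour, since it gives tolerances, yet its area formulas have no place for the hour at which a sample was taken. Followed literally, a concentration measured at one time is integrated at another.

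AUC0-1176, AUC0-∞ and the reticulocyte AUEC are primary endpoints, and CL is dose divided by AUC0-1176. Cohorts have three obligatory volunteers, so one volunteer carries a third of the cohort mean. The stage I PK and PD comparison informs the stage II dose. Volunteers stay on site only for the first 24 h, so every later draw, out to 1176 h, depends on a return visit.

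**Working it through.** The plan states no figure to reproduce. The documents give no PK or PD parameters, so every curve below is an assumption.

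**1. Grids against schedules.** The t_p lists have 18, 20, 21 (PK) and 15 (PD) points. They match the stated ranges of p, and the PK lists equal the nominal hours of the sampling schedules. The axis is therefore nominal, with no transcription error.

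**2. Windows relative to the preceding interval.** In stage I this is 5/30 = 17% at 0.5 h and 1.2% to 4.2% from 8 h onward. In stage II it is 3/15 = 20% at 0.25 h and 5/15 = 33% at 0.5 h ("PK3-2 — 30 ± 5 min after the injection of BCD-131").

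**3. Assumed subcutaneous curve.** C(t) = ka/(ka − k) × (e^(−kt) − e^(−ka·t)) on a unit scale, with ka = 0.03/h and half-life 50 h (k = ln2/50 = 0.01386) or 135 h (k = ln2/135 = 0.00513). The peak is at ln(ka/k)/(ka − k) = 48 h or 71 h.

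**4. All draws inside their windows.** I drew 20,000 sets of uniform timing errors on the 18-point grid. The nominal-time/actual-time AUC ratio lay within 0.993 to 1.007, with mean error near 0 and SD 0.2% (50 h) or 0.1% (135 h). Over a wider set of curves (half-life 25 to 250 h), putting every draw at the same limit of its window gave about ±0.3% to ±0.7% subcutaneously and ±0.4% to ±1.1% intravenously.

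**5. One draw late by δ.** Only the two trapezoids that meet at the late point differ, and the algebra reduces to

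nominal AUC − actual AUC = δ × (C_next − C_previous)/2.

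The sign therefore follows the local direction of the curve. Two cases at half-life 50 h:
- 168 h draw, 24 h late: C(120) = 0.3014 and C(216) = 0.0902. The error is 24 × (0.0902 − 0.3014)/2 = −2.53 on an actual-time AUC of 72.96, or −3.5%.
- 24 h draw, 12 h late: C(8) = 0.2015 and C(48) = 0.5152. The error is 12 × (0.5152 − 0.2015)/2 = +1.88 on 72.09, or +2.6%.

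| Draw | Delay | Half-life 50 h | Half-life 135 h |
|---|---|---|---|
| 24 h | 12 h | +2.6% | +1.4% |
| 168 h | 24 h | −3.5% | −1.4% |
| 336 h | 24 h | −0.5% | −1.1% |
| 504 h | 24 h | −0.3% | −1.1% |

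The concentration assigned to the nominal hour is 11 to 28% too low in the last three rows and 16 to 24% too high in the first. The most extreme case in the wider set of curves was −4.4% (72 h draw, 12 h late, half-life 25 h).

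**6. Effect on k_el, if the regression uses nominal time.** On a log-linear tail with three points and the last one δ = 24 h late, k_el is overstated by δ × (x₃ − x̄)/Sxx, whatever the half-life:
- 216, 288, 336 h: 24 × 56/7296 = 18%
- 288, 336, 504 h: 24 × 128/25728 = 12%
- 336, 504, 672 h: 24 × 168/56448 = 7%

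Half-life is ln2/k_el, so it would be about 7% (1 − 1/1.07) to 16% (1 − 1/1.18) too short. AUC0-∞ hardly moves. At half-life 135 h the tail C(1176)/k is 0.00288/0.00513 = 0.56, on an AUC of 194.2, or 0.3%.

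**7. AUEC.** I assumed baseline 60, a peak rise of 40 to 120 near day 8, and PD windows equal to the PK windows. With every draw at its limit, the in-window error is 0.2 to 0.3%. One 504 h draw 48 h late gives −0.6% to −1.2% on the total reticulocyte area and −2.5% on the area of change from baseline.

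**8. Cohort mean.** With three volunteers of similar AUC, one such draw moves the mean by −3.5/3 = −1.2% to +2.6/3 = +0.9%.

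**The case against.** The strongest reply is that this hardly matters.

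- **In-window error is trivial.** This stands. With perfect timing, the prescribed linear trapezoid already overstates the area under the assumed curves by 0.6% (50 h) to 1.0% (135 h). In-window timing error is of the same order or smaller.
- **The larger figures need implausible delays.** This largely stands. A delay of 24 h is 24 times the ±60 min window at 168 h and 12 times the ±120 min window at 336 h and 504 h. A 12 h delay at 24 h is 36 times the ±20 min window, at the end of the on-site stay. Nothing in the documents suggests that such draws are expected.
- **A reader might infer that day-late samples are kept and treated as on time.** The documents do not say so. The SAP is silent: a day-late draw could be counted as a skipped time point under SAP 7, or picked up by the queries and outlier review in SAP 8.3. What is missing is a stated rule.
- **A reader might infer that AUC is always biased downward.** It is not. The identity in step 5 gives a positive error on the rising limb, and a rising reticulocyte count behaves the same way.
- **A reader might infer that PD draws have no windows.** The supplied protocol is a synopsis that lists only PK sampling times, so the absence of PD windows from this text proves nothing.
- **Actual times do not recover the true area.** This stands. In the six cases with a 24 h delay, actual-time AUC still misses the true area by +0.4% to +1.2%, and in five of them the nominal-time value happens to lie closer. That is cancellation: a downward timing error offsets the trapezoid's upward one. It fails for the early draw at half-life 50 h, where the true area is 72.13. Nominal time gives (72.09 + 1.88)/72.13 = 1.026, and actual time gives 72.09/72.13 = 0.999.

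None of this makes nominal time the better rule.

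**Conclusion.** The point holds as a low-severity improvement. SAP 8.4 sets nominal hours as the time axis for AUC0-1176 and both AUECs while the PK schedule permits departures of ±3 to ±120 min, and no rule covers draws outside the window.

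Under the assumed subcutaneous curves the consequence is below about 1% of AUC in-window, centred on zero. For a single draw 12 to 24 h late it is roughly −3.5% to +2.6% in that volunteer. The 7 to 18% distortion of k_el is doubly conditional: it needs such a draw as the last of three terminal points, and a nominal-time regression that the SAP does not specify. C_max and AC-E_max do not use the time axis and are unaffected.

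The documents do not support a claim that the primary endpoints are materially biased or that the stage II dose choice is at risk from this alone.

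**What to change.** In SAP 8.4:

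1. Define t_p as the actual elapsed time from injection to the recorded draw, with the pre-dose sample set to 0, for AUC, T_max, the k_el regression and both AUECs.
2. Keep nominal hours for by-time tables and mean-profile plots only.
3. Add an end-point rule for a last sample not drawn at exactly 1176 h, for example interpolation, or extrapolation with k_el, to 1176 h for AUC0-1176. In the AUC0-∞ tail, use the actual last time and concentration. State the equivalent rule for AUEC, where k_el does not apply.
4. State how a draw outside its window is handled, and whether it counts as a skipped time point under SAP 7.

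The cost is SAP wording. Checking the stated PK windows already requires recorded draw times; the sponsor should confirm that the PD draw times are recorded too. The change removes the timing error but leaves the linear-trapezoid error of about 0.6 to 1.0%.
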